5.5. Important protocol deviation not leading to elimination from per-protocol analysis set

The following important protocol deviations will be reported by groups:

- Short follow-up: subjects who missed one or more of the site visits and sample collection visits.

6. STATISTICAL ANALYSES

Note that standard data derivation rules and statistical methods are described in annex 1 and will not be repeated below.

6.1. Demography

6.1.1. Analysis of demographics/baseline characteristics planned in the protocol

Demographic (e.g. age at study entry in years, race) and baseline characteristics will be summarized using descriptive statistics.

- Frequency tables will be generated for categorical variables such as race.
- Mean, median, standard error will be provided for continuous data such as age.
- The numbers of withdrawn subjects will be tabulated according to the reason for withdrawal.

6.2. Objectives

6.2.1. Analysis of primary objective

Descriptive statistics will be provided for each primary endpoint at all available time-points and will include (not exhaustive) the following tabulations (with 95% confidence interval [CI]):

- The percentage of CMV seropositive subjects with increase of anti-CMV tegument protein IgG antibodies in serum. An increase will be defined by both a 2-fold or greater increase *and* separately a 4-fold or greater increase in the anti-tegument antibody concentration between subject visits or the last available anti-tegument antibody value if the subject missed a visit or serological results are unavailable.
- The percentage of CMV seropositive subjects with appearance or increase of CMV DNA in urine. A reactivation/reinfection event, based on DNA in the urine, will be defined as any one of the following : (1) the appearance of any detectable CMV DNA by PCR in a sample if CMV DNA was not detected in the previous sample for that subject (2) if the previous sample had CMV DNA detected, but was below the LLOQ for the assay, any value above the LLOQ will be considered a reactivation/reinfection event; and (3) if the previous sample result was above the LLOQ, an increase $\geq 0.5 \log_{10}$ CMV DNA copies/mL in the subsequent sample will be considered an event. It is expected that CMV-positive subjects may have more than one reactivation/reinfection event during the follow up period in this study.

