3. OBJECTIVES

3.1. Primary objective

- To estimate the incidence of CMV secondary infections in seropositive adolescent females.

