4. ENDPOINTS

4.1. Primary endpoints

- Occurrence of CMV secondary infections determined in all seropositive subjects on samples collected during the 4-month Site Visits until study conclusion:
 - Anti-CMV tegument protein IgG antibody concentration in serum (ELISA).
 - Number of CMV DNA copies (pp65 or other genes) in urine (qPCR).

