10.2. Standard data derivation

GSK legacy

- SAS date derived from a character date: In case day is missing, 15 is used. In case day& month are missing, 30June is used.
- Onset day for an event (ae, medication, vaccination, ...): The onset day is the number of days between the last study vaccination & the onset/start date of the event. This is 0 for an event starting on the same day as a vaccination. See SAS date derived in case the start date of the event is incomplete.
- Duration: Duration of an event is expressed in days. It is the number of days between the start & the stop dates + 1. Therefore duration is 1 day for an event starting & ending on the same day.
- Association of an event to the primary epoch: An adverse event belongs to the primary epoch, if the onset date is before and excluding Visit 5 or the last contact date, whichever is coming first.
- Not applicable
- Age: Age at the reference activity, computed as the number of units between the date of birth and the reference activity. Note that due to incomplete date, the derived age may be incorrect by 1 month when month is missing from the birthdate. This may lead to apparent inconsistency between the derived age and the eligibility criteria/the age category used for randomization.
- Conversion of weight to kg
The following conversion rule is used:
 - Weight in Kilogramm= weight in Pounds / 2.2
 - Weight in Kilogramm =weight in oncs / 35.2The result is rounded to 2 decimals.

- Conversion of height to cm

The following conversion rule is used:

- Height in Centimetres = Height in Feet * 30.48
- Height in Centimetres = Height in Inch * 2.54

The result is rounded to the unit (ie no decimal).

- Conversion of temperature to °C

The following conversion rule is used:

- Temperature in °Celsius = ((Temperature in °Fahrenheit -32) *5)/9

The result is rounded to 1 decimal.

- For a given subject and given immunogenicity measurement, missing or non-evaluable measurements will not be replaced. Therefore, an analysis will exclude subjects with missing or non-evaluable measurements.

- The Geometric Mean Concentrations/Titres (GMC/Ts) calculations are performed by taking the anti-log of the mean of the log titre transformations. Antibody titres below the cut-off of the assay will be given an arbitrary value of half the cut-off of the assay for the purpose of GMT calculation. The cut-off value is defined by the laboratory before the analysis and is described in the protocol.

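### The primary objective is an incidence, but SAP 6.2.1 prespecifies only marker-by-marker percentages at time-points, with no whole-follow-up or combined IgG-or-DNA summary

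*SAP*

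**What the plan says.** SAP 3.1 gives one primary objective: "To estimate the incidence of CMV secondary infections in seropositive adolescent females". SAP 4.1 gives the endpoint: "Occurrence of CMV secondary infections determined in all seropositive subjects on samples collected during the 4-month Site Visits until study conclusion". Its two components are serum anti-tegument IgG and urine CMV DNA.

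SAP 6.2.1 then describes the analysis: "Descriptive statistics will be provided for each primary endpoint at all available time-points and will include (not exhaustive) the following tabulations". The listed items, each with a 95% CI, are:

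- the percentage of seropositive subjects with an IgG rise, once at 2-fold or more and once at 4-fold or more, measured "between subject visits or the last available anti-tegument antibody value if the subject missed a visit or serological results are unavailable";
- the percentage with a urine DNA event, under three rules. Rule (1) is "the appearance of any detectable CMV DNA by PCR in a sample if CMV DNA was not detected in the previous sample for that subject". Rule (2) is a move from detected but below the LLOQ to above it. Rule (3) is a rise of at least 0.5 log10 from a value already above the LLOQ.

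The same section adds: "It is expected that CMV-positive subjects may have more than one reactivation/reinfection event during the follow up period in this study". Protocol 8.7.2 has the same structure, plus anti-gB where applicable. SAP 10.1 names intervals only for a proportion (Clopper-Pearson) and for a difference in proportions.

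Protocol 8.3 classifies re-infection and re-activation. Both start from the same list (IgG, anti-gB or urine DNA, joined by AND/OR) and differ in whether strain change is present or absent, subject to assay availability. SAP 6.2.1 does not refer to it.

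**The concern.** An incidence over three years needs three things: what counts as a case, whether a subject counts once or several times, and over what time. The two markers and the event rules are defined. The SAP does not say how the markers combine into one case, or how results at nine follow-up visits become one figure for the follow-up period.

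Percentages by visit and by marker are marginal counts. They do not show whether the subjects positive at Month 8 are the same ones who were positive at Month 4, or whether the IgG subjects are the DNA subjects. Different incidences can therefore produce the same set of tables. If the combined case and the counting rule are settled only once the data are in hand, the answer to the study's one primary question depends on a choice made after seeing the results.

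**Working it through.** **The plan's own figure.** Protocol 8.2 assumes 200 evaluable seropositive subjects, 2% per year and 3 years: 200 × 0.02 × 3 = 12. This reproduces the stated figure of about 12.

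**Inputs.** N = 200 and 12 events (protocol 8.2). Ten Site Visits give 9 follow-up visits, V2 to V10, 4 months apart (protocol 3.1). Assumptions of this review: the 12 events fall as 2, 1, 1, 2, 1, 1, 2, 1, 1 over V2 to V10 (sum 12, or 0.5% to 1.0% per visit), and all 200 subjects complete 36 months.

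**What the tables do give.** For one marker, the counts sum to 12 events. Over 200 × 3 = 600 person-years this is 12/600 = 2.0 per 100 person-years, whoever the subjects are.

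**What they do not give: subjects ever infected.**

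- Maximum: every event is in a different subject. 12/200 = 6.0% (Clopper-Pearson 95% CI 3.1% to 10.2%).
- Minimum under DNA rule (1) alone: the previous sample must be undetected, so no subject has events at two successive visits. The largest sum over two neighbouring visits is 2 + 1 = 3, so at least 3 subjects are needed. Three are enough: V2 A,B; V3 C; V4 A; V5 B,C; V6 A; V7 B; V8 A,C; V9 B; V10 A. 3/200 = 1.5% (95% CI 0.3% to 4.3%).
- Purely logical minimum, where successive events are allowed, as under the IgG rule or DNA rules (2) and (3): the largest single-visit count, 2/200 = 1.0%.

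**First-event rate from the same tables** (events dated at the detecting visit).

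- 12 subjects: the event times in years sum to (2×1 + 2 + 3 + 2×4 + 5 + 6 + 2×7 + 8 + 9)/3 = 57/3 = 19. Person-years = 188 × 3 + 19 = 583. Rate = 12/583 = 2.06 per 100 person-years (exact Poisson 95% CI 1.06 to 3.60). With the simpler denominator of 600 it is 2.0 (1.03 to 3.49).
- 3 subjects: person-years = 197 × 3 + 1/3 + 1/3 + 2/3 = 592.3. Rate = 3/592.3 = 0.51 per 100 person-years (0.10 to 1.48).

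**Across markers.** Suppose 12 subjects ever meet the IgG criterion and 12 ever meet the DNA criterion (assumed). The number meeting either is 12 with full overlap (6.0%) and 24 with none (24/200 = 12.0%, 95% CI 7.8% to 17.3%). Separate tables cannot tell these apart.

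**Does protocol 8.3 fill the gap?** The protocol glossary defines secondary infection as re-activation or re-infection. When the two classes in 8.3 are pooled, the strain condition drops out, because one class requires strain change and the other its absence. What remains is IgG, anti-gB or urine DNA. Anti-gB is a tertiary assay run in a subset. A usable IgG-or-DNA case can therefore be read out of the protocol, but SAP 6.2.1 neither cites it nor tabulates it.

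**The case against.** Much can be said for the plan.

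- *The list is not exhaustive and the shells are in a separate document (SAP 9).* True. A reader might infer that no incidence will be reported, and the documents do not support that. They show only that none is prespecified in the SAP.
- *The wording on time-points could mean cumulative to date.* It is not excluded. It is also not stated, and the event definitions compare each visit with the one before. A cumulative reading would still give no combined case.
- *Incidence may mean all events, and 6.2.1 expects repeats.* For one marker, the visit counts do yield an approximate all-event rate, so it would be wrong to say that the tables carry no information on incidence. The objection does not cover the first-event rate, the proportion ever infected or the combined case.
- *The protocol already joins IgG and DNA.* This stands. A reader might infer that the case is wholly undefined, or that the strain condition blocks it. Neither follows from 8.3.
- *The fold threshold is fixed.* Both thresholds will be tabulated. Only the choice of headline is open.
- *Follow-up is handled.* In part. Protocol 7.2 uses all data up to withdrawal. Protocol Table 4 and SAP elimination code 2090 keep attended visits near schedule, and code 2500 addresses missing Year 1 results in seropositive subjects. Against that, SAP 5.5 keeps some subjects in the per-protocol set: "Short follow-up: subjects who missed one or more of the site visits and sample collection visits". SAP 10.2 says "an analysis will exclude subjects with missing or non-evaluable measurements". Neither rule states the time at risk.
- *The study is descriptive (SAP 7).* No error rate or power is affected, and subject-level data would allow the figures to be computed later.

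**Conclusion.** The point holds as a gap in prespecification, and it should be fixed. Following SAP 6.2.1 exactly gives no proportion ever infected, no first-event rate and no IgG-or-DNA incidence, although incidence is the only primary objective.

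At the plan's scale, identical visit tables fit 1.5% to 6.0% of subjects ever infected under DNA rule (1), a four-fold range. Combining markers can add up to a further factor of two. These figures rest on the assumed spread of the 12 events and on complete follow-up. The lower end also needs a few subjects to alternate between detected and undetected for three years, so the range shows what the tables leave open and is not a forecast. Assuming 2% per visit would give a wider range (36 events, 2.0% to 18.0%), but the plan assumes 2% per year.

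The documents do not support the stronger conclusions that the incidence cannot be estimated, that the protocol lacks any combined case, or that the sample-size arithmetic is wrong.

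**What to change.** In SAP 6.2.1:

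- Define the primary case as an IgG rise or a urine DNA event at a Site Visit, that is, the common front end of protocol 8.3 without anti-gB. Report it with the 2-fold and with the 4-fold threshold, and name one in advance as the headline.
- Report the first-event rate per 100 person-years with an exact Poisson 95% CI, and the 36-month cumulative incidence with a 95% CI.
- Use one time-at-risk rule: from Visit 1 to the first event or the last Site Visit with at least one evaluable marker, with events and time taken from the same visits. As a sensitivity analysis, end follow-up at the last visit with both markers evaluable and count no event after it.

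In SAP 6.2.2, add the first-seroconversion rate per 100 person-years, since the secondary objective is also an incidence. Keep the per-visit tables as supportive. Kaplan-Meier event dating, an episode rule for repeat events and a subject-clustered variance are optional.

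The cost is some SAP text, a few extra tables from data already collected, and an advance commitment to one headline case.

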5.4.1.1. Excluded subjects

A subject will be excluded from the ATP analysis under the following conditions

Code	Condition under which the code is used
1040	Administration of concomitant vaccine(s) forbidden in the protocol (see also eligibility criteria)

	CDM responsibility from review of individual data listings
2010	Protocol violation linked to the inclusion/exclusion criteria including age and excluding codes mentioned below.
2040	Administration of any medication forbidden by the protocol Responsibility of CRDL following review of individual data listings
2050	Underlying medical condition forbidden by the protocol Responsibility of CRDL following review of individual data listings
2070	Concomitant infection not related to the vaccine which may influence immune response Responsibility of CRDL following review of individual data listings
2090	Blood samples taken but: non-compliance with blood sampling schedules (dates of BS not corresponding to adapted protocol intervals or unknown BS)
	When a visit and/or a vaccination and/or a blood sample is Not Done/Performed, only the code 2100 is attributed to the subject.
2100	Serological results not available (including lost samples, blood sample not done, unable to test, absence of parallelism). elimination code if ALL are missing
2500	Other: For seropositive subjects only: Serological results not available for anti-CMV tegument protein IgG at the 4 site visits (Visit 1 to Visit 4) and from at least 2 sample collection visits during Year 1
3500	Urine and saliva samples taken but: non-compliance with blood sampling schedules (dates of BS not corresponding to adapted protocol intervals or unknown BS)

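### Per-visit percentages in SAP 6.2.1, mainly for the IgG increases, mix comparison intervals of unequal length after a missed visit, so they are not strictly comparable between visits or convertible to an incidence

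*SAP*

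**What the plan says.** - **Reporting.** SAP 6.2.1: "Descriptive statistics will be provided for each primary endpoint at all available time-points", as percentages with 95% confidence intervals. The objective (SAP 3.1) is to estimate incidence.
- **IgG comparator.** A 2-fold and, separately, a 4-fold rise is judged between visits, "or the last available anti-tegument antibody value if the subject missed a visit or serological results are unavailable".
- **Urine comparator.** New CMV DNA counts "if CMV DNA was not detected in the previous sample for that subject". No interval is stated.
- **Missing results.** SAP 10.2: "missing or non-evaluable measurements will not be replaced. Therefore, an analysis will exclude subjects with missing or non-evaluable measurements".
- **Who stays in the per-protocol set.** When a visit is not done, SAP 5.4.1.1 assigns only code 2100, whose condition is "elimination code if ALL are missing". SAP 5.5 lists among the deviations that do not eliminate: "Short follow-up: subjects who missed one or more of the site visits and sample collection visits".
- **Year 1.** For seropositive subjects only, code 2500 eliminates on "Serological results not available for anti-CMV tegument protein IgG at the 4 site visits (Visit 1 to Visit 4"; a condition on two Year 1 Sample Collection Visits is attached. Years 2 and 3 have no counterpart.
- **Schedule.** Blood is drawn about every 4 months. Protocol Table 4 allows 10 days either side for each Site Visit.

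**The concern.** Taken together, these rules let a subject leave the denominator at a visit she misses and return at the next one with an older comparator. One visit's percentage then pools comparisons over 4, 8, 12 or more months. The numerator reflects different lengths of time, while the denominator counts each subject once.

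For IgG the gap also changes what counts as an event. Two successive 1.5-fold rises give no 2-fold event on 4-month comparisons. If the middle visit is missed, the same subject shows 1.5 x 1.5 = 2.25-fold, which is an event. Conversely, a rise that wanes before the next sample is lost.

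At stake is how the tables are read. A difference between two visits may partly reflect attendance, and a visit percentage cannot be turned into a rate by assuming 4 months at risk.

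**Working it through.** **The plan's own figure.** Protocol 8.2 expects about 12 re-infected subjects from 200 evaluable subjects at 2% per year over 3 years: 200 x 0.02 x 3 = 12.0, or 200 x (1 - 0.98^3) = 11.8. The figure reproduces. The documents give no figure for intermittently missed visits or for per-visit intervals.

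**Which visits are affected.**
- If code 2500 requires a result at each of Visits 1-4, Visit 5 always looks back to Visit 4. Visit 6 is the first that can mix intervals.
- If code 2500 removes only subjects with no result at any of Visits 1-4, mixing starts at Visit 3. SAP 5.5, which has no Year 1 exception, fits this reading better.
- Code 2500 concerns serology, so it secures nothing for urine in Year 1 on either reading.

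**Mean interval.** Assume each visit not otherwise required is missed independently with probability m. Visits that are attended stay close to schedule, so gaps are multiples of 4 months. Under the first reading, among attenders at Visit k (k at least 6):

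mean interval = 4 x (1 + m + ... + m^(k-5)) months, with limit 4/(1-m).

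**Event percentage if the signal persists.** At annual rate r, sum over gaps of j visits: P(gap j) x (1 - exp(-r x 4j/12)). The 4-month value at 2% per year is 0.6644%.

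| Assumed m | Mean interval, Visit 6 | Mean interval, Visit 10 | Ratio to 4 months | Visit 10 percentage at 2%/year | Excess (points) | Excess events per 200 |
|---|---|---|---|---|---|---|
| 5% | 4.20 | 4.21 | 1.05 | 0.6992 | 0.03 | 0.07 |
| 10% | 4.40 | 4.44 | 1.11 | 0.7377 | 0.07 | 0.15 |
| 20% | 4.80 | 5.00 | 1.25 | 0.8291 | 0.16 | 0.33 |

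For scale, the exact 95% interval for 1 event in 200 is 0.01% to 2.75%.

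**Shape.** At m = 10% the mean intervals at Visits 5-10 are 4.0, 4.4, 4.44, 4.44, 4.44 and 4.44 months: a step, then a plateau. A continuing rise needs missingness that itself grows. With an assumed 5% at Visit 5 rising to 25% at Visit 9, the mean goes from 4.2 months at Visit 6 to 5.2 at Visit 10.

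**Second reading of code 2500.** At m = 10% the means are 4.0 at Visit 2, 4.4 at Visit 3 and 4.44 from Visit 4. More visits are mixed, but the contrast between Year 1 and later visits largely disappears.

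**If the signal is transient.** Take onset rate a = 0.02/12 per month and resolution rate b = 1/(mean duration in months). The chance that a signal absent at the comparator is present d months later is a/(a+b) x (1 - exp(-(a+b)d)). The Visit 10 average divided by the 4-month value, for m = 10% and 20%:
- mean duration 1 month: 1.002 and 1.004
- 2 months: 1.014 and 1.028
- 4 months: 1.038 and 1.079
- 12 months: 1.077 and 1.166

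**Higher event rates.** The 2% is described as re-infection, whereas the endpoint also counts re-activations, so events may be more frequent; the documents give no figure. At an assumed 10% per year with a persistent signal, 3.28% becomes 3.45%, 3.63% and 4.06% for m = 5%, 10% and 20%. At an assumed 30% per year, 9.52% becomes 9.97%, 10.46% and 11.62%.

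**The case against.** The look-back is a sensible choice. It avoids losing a persistent rise because a visit was missed, and that suits an endpoint defined as occurrence until study conclusion. SAP 7 calls all analyses descriptive, no trend test between years is planned, and nothing in the SAP adds visit percentages together. The listed tabulations are not exhaustive, and the table shells are in a separate document that was not available, so intervals or cumulative figures may be shown there. SAP 5.5 already has missed visits reported by group. At the only rate in the documents, the effect is far inside the sampling error of one visit's percentage.

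Most of this stands, and it makes the point minor. It does not remove it: the definition in SAP 6.2.1 still pools unequal intervals, and the SAP text provides no denominator that would yield the incidence named in the objective.

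A reader might go further and infer that percentages after Year 1 drift upward by construction because completeness is enforced only in Year 1. The documents do not support that, for four reasons:
- The Year 1 contrast rests on one reading of code 2500, which sits badly with SAP 5.5 and covers serology only.
- Constant missingness gives a step and a plateau, not a drift.
- The stated 15-20% drop-out lengthens no interval, because those subjects leave and do not return.
- The direction is not fixed, since a waning signal is lost across a long gap.

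**Conclusion.** The point holds as one of comparability and should be graded minor. Whenever a subject intermittently misses a Site Visit or a result, the visit percentages pool comparison intervals of unequal length, with no adjustment. IgG carries the point; for short urine shedding the effect is almost nil.

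The 5-25% relative inflation for m between 5% and 20% is an upper bound. It assumes independent missed visits at a constant rate that the documents do not give, and signals that persist to the next sample. In absolute terms it is 0.03-0.16 percentage points at 2% per year, and larger only if secondary events are much more frequent. The number of visits affected cannot be settled until code 2500 and SAP 5.5 are reconciled.

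**What to change.** In SAP 6.2.1:
1. Base each visit's IgG and urine DNA percentage on subjects with a result at that Site Visit and at the immediately preceding scheduled Site Visit.
2. Show events found against an older comparator on a separate line, with the length of the gap.
3. Keep those events in any incidence over the whole follow-up, with time since the comparator sample as the time at risk, so that no event is discarded.

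In SAP 5.4.1.1 and 5.5, state whether code 2500 applies when any Visit 1-4 result is missing or only when all are, and make the two sections agree.

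The cost is SAP wording, one extra table line and slightly smaller per-visit denominators. No new data are needed.

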3.1. Discussion of study design

The study sites will be selected in multiple countries, including countries where the CMV prevalence is assumed to be high in order to enroll primarily CMV seropositive adolescent females to allow the evaluation of CMV secondary infections. Since enrolment will proceed without previous CMV screening, some of the enrolled subjects will be seronegative. The enrolled seronegative subjects will allow the estimation of the incidence of CMV primary infections in the adolescent population.

To increase the probability to capture all CMV infections (primary and secondary infections), regular sample collection time-points have been arranged:

- **Site Visits:** Subjects will be asked to perform a Site Visit approximately every 4 months for 3 years (10 Site Visits in total). At Site Visits, blood, urine and saliva will be collected.
- **Sample Collection Visits:** Subjects will be contacted to perform urine and saliva sample collections at home either by self-collection or by a home visiting nurse. Alternatively subjects may be asked to come back to the study center where the investigator or designate will collect the samples. These Sample

Collection Visits will occur approximately every 4 months for 3 years between 2 Site Visits (9 Sample Collection Visits in total).

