8.2. Sample size consideration

The sample size for this study is not based on formal statistical considerations. The target is to recruit approximately 200 evaluable seropositive adolescent females. Considering a conservative incidence rate of CMV infection of 2% per year, it is expected that approximately 12 seropositive subjects will be re-infected during the study period.

A target number of approximately 200 evaluable seropositive adolescent females will be analyzed. Considering a 15-20% drop out rate during the 3-year study period, approximately 240 seropositive subjects will be enrolled.

Some laboratory assays will be performed on a subset. The subset will be defined based on the outcome of the primary/secondary endpoints or the development of the assay. The subset is the minimum number of subjects that will be tested. If applicable, all subjects could be tested.

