8.5. Derived and transformed data

Immunogenicity

The cut-off value is defined by the laboratory before the analysis and is described in [Table 6](#).

- A seronegative subject is a subject whose titer is below the cut-off value.
- A seropositive subject is a subject whose titer is greater than or equal to the cut-off value.

For seronegative subjects, seroconversion is defined as the appearance of antibodies (i.e. titer greater than or equal to the cut-off value).

The geometric mean titers (GMTs) calculations will be performed by taking the anti-log of the mean of log titer transformations. Antibody titers below the cut-off of the assay will be given an arbitrary value of half the cut-off for the purpose of GMT calculation.

Virology

For seronegative subjects, CMV DNAemia is defined as the detection of CMV DNA (i.e. number of CMV DNA copies/mL is greater than or equal to the cut-off value).

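### The urine-DNA event rule sets no minimum rise or confirmation around the assay limits, so a seropositive subject with an unchanged low viral load can be counted as an incident secondary infection

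*SAP*

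**What the plan says.** SAP 6.2.1 gives three routes to a urine-DNA event in a seropositive subject.

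- **Rule (1), from undetected:** "the appearance of any detectable CMV DNA by PCR in a sample" is an event "if CMV DNA was not detected in the previous sample for that subject".
- **Rule (2), from detected but below the LLOQ:** "any value above the LLOQ will be considered a reactivation/reinfection event".
- **Rule (3), from above the LLOQ:** the next sample must be at least 0.5 log10 copies/mL higher.

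The SAP adds that "CMV-positive subjects may have more than one reactivation/reinfection event during the follow up period". The primary endpoint (SAP 4.1) is "determined in all seropositive subjects on samples collected during the 4-month Site Visits until study conclusion", and Protocol 3.1 sets a "Site Visit approximately every 4 months for 3 years (10 Site Visits in total").

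For the other primary component, anti-tegument IgG, SAP 6.2.1 defines two separate counts, one at a 2-fold and one at a 4-fold increase. The DNA component has one count only.

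**The concern.** Rule (3) shows that the SAP does not treat a small upward change between two samples as a new event. That protection is absent where it is most needed. Near the detection limit a sample with constant true load is sometimes detected and sometimes not, and near the LLOQ it falls sometimes below and sometimes above. Rules (1) and (2) turn each upward crossing into an event, without a minimum rise, a replicate or a second positive sample.

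Nothing later in the plan removes such an event. Protocol 8.3 links urine DNA to the serological criteria by and/or, and makes the strain evidence conditional on the assays being available. DNA alone can therefore make a case. The primary objective is the incidence of secondary infection, so stable low-level shedding or an isolated false detection would be reported as incidence. No stricter count is planned that would show how much of the result depends on these crossings.

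**Working it through.** **The plan's own figure.** Protocol 8.2 has 200 evaluable seropositive subjects and states: "Considering a conservative incidence rate of CMV infection of 2% per year, it is expected that approximately 12 seropositive subjects will be re-infected". Check: 200 × 0.02 × 3 = 12.0. As a cumulative risk, 200 × (1 − 0.98³) = 11.8. The figure reproduces. It concerns re-infection only and serves here as context.

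**Inputs.** Ten Site Visit samples per complete subject, hence 9 consecutive pairs (Protocol 3.1), and the event rules of SAP 6.2.1. Assumed, because the documents give no value: a detection probability p per sample that is constant for a subject with constant load, independent results between visits, all 10 samples available, and a count cumulated over follow-up.

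**Chance of at least one rule-(1) event.** The only sequences of 10 results without an undetected-to-detected step are runs of detected followed by runs of undetected. So

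P(at least one event) = 1 − Σ p^a (1 − p)^(10−a), a = 0, …, 10.

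At p = 0.5 every term is 1/1024 and there are 11 terms: 1 − 11/1024 = 98.9%. The expected number of events per subject is 9p(1 − p). At a single visit with one predecessor the chance is p(1 − p).

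| p | At least one event, 10 visits | Mean events | Single visit |
|---|---|---|---|
| 5% or 95% | 36.8% | 0.43 | 4.8% |
| 10% or 90% | 60.8% | 0.81 | 9% |
| 20% or 80% | 85.7% | 1.44 | 16% |
| 30% or 70% | 95.1% | 1.89 | 21% |
| 50% | 98.9% | 2.25 | 25% |

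With fewer samples at p = 0.5 the chance is 93.8% for 7 samples and 68.8% for 4.

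**Rule (2).** The same formula applies to a subject who is always detected and whose true load sits at the LLOQ. Each value then falls above or below with probability 50%, so about 99% would have at least one event over 10 visits.

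**Isolated false detections.** For truly negative samples with an assumed false-detection rate f, the expected number of subjects with an event over 9 intervals is 200 × (1 − (1 − f)^9):

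- f = 0.1%: 1.8 subjects
- f = 0.5%: 8.8 subjects
- f = 1%: 17.3 subjects

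**What a stricter count would do.** Take a constant load at the LLOQ and an assumed assay SD of 0.1, 0.2 or 0.3 log10. Simulation gives about 99% of subjects with an event under the current rules. Under a 0.5 log10 rise, with previous values below the LLOQ set to the LLOQ, the figures are about 0%, 3% and 25%. From such a previous value an event needs at least 10^0.5 = 3.16 times the LLOQ.

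**The case against.** The strongest reply is that the size of the problem cannot be established. The documents give no detection limit, no LLOQ, no assay specificity and no share of persistent low-level shedders. This stands: the figures above are conditional, not an estimate of bias.

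A second reply is that SAP 6.2.1 tabulates by time-point and does not spell out a cumulative percentage. This also stands, and at one visit the chance for a constant shedder is at most 25%. But the objective is incidence, and the SAP itself speaks of repeat events over follow-up, so a cumulative reading is natural.

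A third reply is that the plan leaves room for more. Its tabulations are described as not exhaustive, Protocol 8.3 allows several case definitions to be explored, all analyses are descriptive (SAP 7), and copy numbers will be summarised. None of this commits the sponsor to a stricter DNA count. Rule (1) does implement the protocol's criterion of appearance of DNA in urine, which is a reason to keep it, but not to report it alone. Rule (2) does contain a quantification threshold, but no minimum rise across it.

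Three stronger readings are tempting and are not supported:

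- **That a shedder near the detection limit is almost certain to be counted.** A chance of 95% or more needs a per-sample detection probability of about 30% to 70%, independent results, nearly all 10 visits and a cumulative count. The documents fix none of these except the visit schedule.
- **That false cases can be set directly against the 12 expected.** Those 12 are re-infections at a rate the protocol calls conservative, whereas the DNA endpoint also counts re-activations.
- **That seronegative subjects are held to a different threshold on the same assay.** Protocol 8.5 defines detection for them as "number of CMV DNA copies/mL is greater than or equal to the cut-off value", but gives no value. SAP 6.2.3 speaks only of presence of DNA in urine. A difference is not shown.

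**Conclusion.** The point holds as a gap in the primary endpoint definition. If the plan is followed exactly, a seropositive subject with unchanged low viral load can be counted as an incident secondary infection, possibly more than once, and no planned count would reveal it. Under the stated assumptions the chance for such a subject ranges from about 37% to 99% over 10 Site Visits as detection per sample varies between 5% and 95%. The effect on the reported percentage is unknown. With an assumed false-detection rate of 0.1% to 1% per sample, about 2 to 17 subjects per 200 would be added over the study. That uncertainty is the argument for a sensitivity count: it should be added, but the current rule need not be withdrawn.

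**What to change.** In SAP 6.2.1, tabulate the seropositive urine-DNA endpoint twice, in the same way as IgG:

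- **(a)** the current three-part rule, unchanged;
- **(b)** a quantifiable-rise rule: an increase of at least 0.5 log10 copies/mL over the previous value, with previous values that are undetected or below the LLOQ set to the LLOQ. From such a value an event then needs about 3.2 × LLOQ or more, and the SAP should say so.

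The cost is one derived variable and one table, with no new samples or tests. Count (b) will miss true low-level shedding and modest new quantifiable shedding up to about 3.2 × LLOQ. That is why (a) stays. Count (b) also does not remove all noise if assay variability is large (about 25% of constant-load subjects at the LLOQ with an assumed SD of 0.3 log10). The gap between the two counts shows how far the result depends on detections near the limits.

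Rule (b) should be confined to seropositive subjects. Seronegative subjects have viral load tested only upon seroconversion (Protocol Tables 7 and 8), so the previous value it needs would generally be missing.
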